4.4.3. Route of Trial Intervention

Intervention is taken orally. Cholera is a gastrointestinal disease; the oral route is by far the most common route of drug administration in gastrointestinal diseases.

4.4.4. Dosing and Administration

Cholera typically presents with voluminous liquid stool due to hypersecretion of fluids by the intestine²¹. VR-AD-1005 is not absorbed and acts at the level of intestinal mucosa. Thus, first dose of the drug is dissolved in much larger than normal volume of fluid presented in the intestine of a patient recently admitted for cholera. In addition, due to the diarrhea, first dose of the drug is evacuated with stool faster than subsequent doses. In order to maintain working concentration and counteract dilution, first dose of the drug is tripled, representing the "loading dose" drug administration tactics. The remaining doses are single doses for the three days which is in line with average duration of the cholera episode and thus gives sufficient time for the drug to exert its effect. The treatment will be administered to participants under the supervision of trained study personnel, i.e. study nurse. Nurses will be instructed to monitor for vomiting or accidental loss of treatment dose (for example, dropped dose). The participants will be instructed to swallow the treatment whole without chewing with a glass of water or oral rehydration solution. The volume of the liquid will be registered in the water intake charts.

Administration begins when the patient is able to swallow the tablet. If the patient vomits less than 30 minutes after administration of dose, the dose will have to be re-administered after about 15 minutes. If the patient vomits after 40 minutes, the clinician will check the vomitus to see if the medication is in there, if the medication is not visible then the dose is not re-administered. If the medication is visible, then the dose is re-administered after 15 minutes. Both arms will receive extra doses of the medication for these purposes. In the event of lost dose, the pharmacy will have a backup of the medication doses for emergency purposes.

VR-AD-1005 oral dose will be administered orally 4 times per day (approximately every 4-5 hours with overnight break to allow for participants rest and recovery) with first administration of 3 capsules as loading dose. Dosing is indicated in the table below (**Table 3**), with reasonable timing of administration at 7:00, 12:00, 17:00 and 21:00 hours \pm 1 hour.

Table 3: VR-AD-1005 doses and dosing schedule

Time	Day 1	Day 2	Day 3
Time 0 hr	3 doses	1 dose	1 dose
Time +5:00 hr	1 dose	1 dose	1 dose
Time +10:00 hr	1 dose	1 dose	1 dose
Time +15:00 hr	1 dose	1 dose	1 dose

4.4.5. Access to Trial Intervention After End of Trial

After the end of trial, IP will no longer be accessible to the participants. Cholera is an acute infectious disease, and after resolution of cholera episode treatment is no longer warranted.

4.4.6 Participant Assignment, Randomization and Blinding

4.4.6.1. Participant Assignment

During recruitment, in addition to rehydration/antibiotics, each eligible participant will receive a numbered individual package of treatment, with package number being unique to the particular participant. After the end of the study for the purpose of data analysis the randomization tables will be supplied to the biostatisticians and data from all participants who have completed the trials will be assigned to the Group A (VR-AD-1005 intervention) or Group B (placebo) for analysis.

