4.6. Start of Trial and End of Trial

Trial starts once the participant has signed the informed consent form. The end of trial is defined as database lock after completion of the study by the last patient. A participant is considered to have completed the study if he or she has completed all phases of the study including the last visit or the last scheduled procedure shown in **Appendix I**.

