4.12. Lost to Follow-up

A participant will be considered lost to follow-up if he or she fails to return for three out of four scheduled phone calls or one missed in-person visit (for withdrawals) and is unable to be contacted by the study site staff. The following actions must be taken if a participant fails to return to the clinic for a required study visit: The site will attempt to contact the participant and reschedule the missed visit within 7 days and counsel the participant on the importance of maintaining the assigned visit schedule and ascertain if the participant wishes to and/or should continue in the study.

Before a participant is deemed lost to follow-up, the investigator or designee will make every effort to regain contact with the participant (where possible, 3 telephone calls and/or electronic messages, one home visit). These contact attempts should be documented in the participant's medical record or study file.

Should the participant continue to be unreachable, he or she will be considered to have been lost to follow-up and will be excluded from the long-term safety data analysis.

Since follow-up occurs after the completion of the treatment course, loss to follow-up is not critical for the primary and secondary endpoints and treatment data obtained during the course of the trial will remain valid.

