6.0 Data Analysis

Describe plans for data analysis, including stratification by sex, gender and diversity. Indicate whether data will be analysed by the investigators themselves or by other professionals. Specify what statistical software packages will be used and if the study is blinded, when the code will be opened. For clinical trials, indicate if interim data analysis will be required to determine further course of the study.

Data analysis must comply with ICH E9 Guideline and ICH E9(R1) Guideline. All relevant data collected in the trial should be considered in the statistical considerations section.

The analysis will be conducted on all participant data at the time the trial ends.

Statistics for primary end-point data and parametric secondary end-point data will be presented via means (alternatively, LSMEANS) with standard deviations; primarily two-tailed Student's t-test will be used for analysis with significance level of $p \leq 0.05$. For non-parametric analysis, such as lifetime data, Kaplan-Meier analysis will be used with significance level of $p \leq 0.05$. Some data might be expressed and analyzed as % values, such as the occurrence of unscheduled IV rehydration.

Analysis of secondary endpoints will be performed through the same method of the primary endpoint, which is found via a one- sided two sample unequal variance Student's t-test. The scale for each secondary endpoint will be nominal and will be determined at a single endpoint, which is at the end of intervention. The results will be presented by LSMEANS (Least-squares Means) with standard errors.

Primary Endpoint:

Reduction in stool output volume (ml/hour) over a treatment period measured and plotted as total stool output during 12-hour stool collection at every 12 hours for 72 hours.

Secondary Endpoints:

- Time until the stool volume output of 200mL/hour or less. Duration of stool output in excess of 200mL/hour per patient will be recorded between the start and end of the treatment for both treatment groups.
- Time until recovery. Duration of diarrhea until the passage of first non-watery stool or no stool for 12 hours or the end of treatment (72 hours) will be derived from date and time records in daily stool charts.

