6.2. Analysis Supporting Primary Objectives

6.2.1. Statistical Model, Hypothesis, and Method of Analysis

Primary Endpoint:

Reduction in stool output volume over a treatment period.

Primary Endpoint 1., Hypothesis 1. Treatment with VR-AD-1005 reduces stool output in patients with diarrhea due to *V. cholerae* infection. Null hypothesis is stated as no statistically significant difference in stool output volume as compared to placebo; alternative Hypothesis 1 is stated as statistically significant reduction in stool output volume in patients treated with VR-AD- 1005.

Two analytical approaches are proposed. Approach 1 will be based on the total quantity of stool purged by participant during the intervention administration period. Stool output will be expressed as g/kg body weight based on the stool charts, and the means will be compared between intervention and placebo groups using Student's unpaired t-test. In approach 2, stool purging is measured and plotted as total stool output in ml/kg/12 hours based on the individual stool collection charts. Weight of stool will be converted to volume using 1:1 weight/volume ratio. Diarrhea of cholera resolves rapidly, and majority of patients are expected to recover within 30-50 hours after randomization. 12-hour analysis increments allow a better insight into the onset and timing of the effect of study intervention as compared to cumulative data over the duration of the treatment. Means will be compared for each 12-hour period after first intervention administration using unpaired Student's t-test. Normal distribution is assumed for both cases. Analysis will be conducted in the ITT, MITT and PP groups. Missing data and outliers will be handled using imputation technique. Non-adherence and lost to follow-up patients will be categorized into the appropriate group and handled accordingly. No subtractions will be made from the ITT group after randomization assignment.

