6.2.2. Handling of Missing Data

Missing data other than protocol-planned baseline values will be classified as missing completely at random (MCAR) or missing at random (MAR). MCAR can be confirmed by partitioning the data into two parts: one set containing the missing values, and the other containing the non-missing values. After partitioning the data, the t-test of mean difference is carried out in order to check whether there exists any difference in the sample between the two data sets. If the number of missing values is small, i.e. if the number of the cases is less than 5% of the sample, then the researcher can drop them. Otherwise, when analyzing using ITT population, model based multiple imputation (MI) will be used for both primary and secondary outcomes. The number of imputations will be the largest value of:

- 10, or
- The proportion of missing values for the actual variable * 100.

200 burn in iterations will be used for all analyses. Trace plots and distribution plots will be created to check the accuracy of imputations.

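### Section 4.4.6.1, read literally, gives an arm for analysis only to participants who completed the trial, which contradicts the ITT rule in section 6

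*Combined protocol and SAP*

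**What the plan says.** Section 4.4.6.1 describes what happens at the end of the study. The statisticians receive the randomisation tables, after which "data from all participants who have completed the trials will be assigned to the Group A (VR-AD-1005 intervention) or Group B (placebo) for analysis". In the text available, no other section says whose data are linked to an arm at unblinding.

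Section 4.6 defines completion: "A participant is considered to have completed the study if he or she has completed all phases of the study including the last visit". The sentence goes on to offer, as an alternative to the last visit, the last scheduled procedure in Appendix I.

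Section 6 takes a different line:

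- Section 6.0: "The analysis will be conducted on all participant data at the time the trial ends".
- Section 6.2.1: "Analysis will be conducted in the ITT, MITT and PP groups", and "No subtractions will be made from the ITT group after randomization assignment". Section 6.3 repeats both for the secondary endpoints.
- Section 6.2.2: unless fewer than 5% of cases are missing, "when analyzing using ITT population, model based multiple imputation (MI) will be used for both primary and secondary outcomes".
- Section 6.4: the proportions with an AE or SAE are taken over all participants in each arm.

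**The concern.** Completion is settled after randomisation. Section 4.11 lets the investigator withdraw a participant for adverse events, disease progression, non-compliance or inability to receive the intervention for three days. Section 4.4.6.3 withdraws a patient whose code is broken in an emergency. Any of these can depend on the treatment or on how heavily the patient is purging. Section 4.11 also says that participants withdrawn after dosing are not replaced.

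If the arm is attached only to completers, the primary comparison is made in groups selected after randomisation and loses the protection that randomisation gives. ITT membership and the primary set are not defined in the text available; section 5.0 gives only a planned ITT size of 150. An analyst who meets the two instructions therefore has no rule for choosing between them. If the choice is made after the codes are open, it can be made knowing the result.

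**Working it through.** **1. The texts side by side**

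| Step | Section 4.4.6.1 with 4.6 | Section 6 |
|---|---|---|
| Who has an arm | Those who completed the trial | Everyone randomised (ITT, nothing subtracted) |
| Withdrawn after dosing | No arm assigned | Kept in ITT; missing outcomes imputed |
| Safety denominator | Completers, if taken literally | All participants per arm |

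Imputing an outcome for a withdrawn patient and counting that patient in an arm's denominator both need the arm to be known. Section 6 therefore cannot be carried out on a dataset built as 4.4.6.1 describes.

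**2. The plan's own power figures (section 5.0)**

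Inputs: mean 280 g/kg, SD 156 g/kg, 33% reduction, two-sided alpha 0.05.

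- Difference = 0.33 × 280 = 92.4 g/kg.
- Noncentrality = 92.4 / (156 × √(2/n)): 2.96 at n = 50 and 3.63 at n = 75 per arm.
- Power from the noncentral t: 0.835 (plan: 0.82) and 0.950 (plan: 0.94). Both reproduce to within 2 percentage points.

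**3. Is the risk one of power?**

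No dropout rate is stated, so the rates here are assumptions. By the normal approximation, power is 0.952 with 75 per arm. With 5%, 10%, 20% and 33% loss in both arms it is 0.942, 0.931, 0.901 and 0.842. It stays above 0.80 throughout, so the risk is bias.

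**4. Illustration A: loss in one arm (all assumed)**

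Suppose k of 75 patients do not complete and average 1 SD (156 g/kg) above the mean of the full arm. The completers' mean is then too low by k × 156 / (75 − k).

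| Loss | k | Shift (g/kg) | Share of 92.4 |
|---|---|---|---|
| 5% | 4 | 4 × 156 / 71 = 8.8 | 10% |
| 10% | 8 | 8 × 156 / 67 = 18.6 | 20% |
| 15% | 11 | 11 × 156 / 64 = 26.8 | 29% |

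**5. Illustration B: unequal loss with no treatment effect (all assumed)**

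Both full arms have mean 280 g/kg. Non-completers have mean m × 280, and a fraction f is lost: 15% on placebo, 5% on active. Completers' mean = (280 − f × m × 280) / (1 − f).

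- m = 1.5: placebo (280 − 63) / 0.85 = 255.3; active (280 − 21) / 0.95 = 272.6; difference 17.3 g/kg.
- m = 2: placebo (280 − 84) / 0.85 = 230.6; active (280 − 28) / 0.95 = 265.3; difference 34.7 g/kg.
- 10% loss in both arms, same m: difference 0.

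In this example the bias runs against the drug. Swapping the two loss rates makes it favour the drug by the same amount.

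**The case against.** The strongest case against is that 4.4.6.1 is an operational sentence about handing over the tables. It defines no analysis set and does not contain the word only. The analysis is governed by section 6, which asks for ITT more than once. Other sections also presuppose an arm for dropouts: 4.1 examines reasons for dropout as indicators of treatment differences, 4.11 sets out a full assessment at discontinuation, and 7.1 keeps the data of withdrawn participants in the database. All of this stands, and it rules out three stronger readings.

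- **That the analysis as planned is completers-only.** A reader might infer this from 4.4.6.1 alone. Section 6 prescribes ITT, MITT and PP, and imputation in the ITT population would have little purpose among completers.
- **That non-completers vanish from the safety analysis.** Section 6.4 uses all participants per arm and lists adverse events that led to discontinuation.
- **That a patient with full stool data who later misses the follow-up calls loses an arm.** The Appendix I schedule ends at end of treatment and shows no calls. Section 4.11 describes calls to patients who have already completed the protocol. Section 4.12 says of those lost to follow-up that "treatment data obtained during the course of the trial will remain valid". Such a patient probably counts as a completer.

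It is also fair to say that the illustrations rest on chosen assumptions. Section 4.3 keeps all participants as inpatients for the three days, so loss of 10% to 15% in one arm is not something the documents predict. Non-completers could also be lighter purgers.

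What the objection does not remove is the conflict itself. The one sentence on linking data to arms names a group chosen after randomisation, and nothing in the text available says that section 6 overrides it.

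**Conclusion.** The point holds as an internal contradiction that needs correcting. Read literally, 4.4.6.1 leaves withdrawn and discontinued participants without an arm, and the ITT rule, the imputation and the safety denominator in section 6 cannot then be applied to them. It does not show that the sponsor intends a completers-only analysis.

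The size and direction of any bias are unknown. The 9 to 27 g/kg and 17 to 35 g/kg figures show only what assumed loss patterns would do, and they fall to zero when loss is equal and similar in the two arms. The stated power is not in question.

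Section 4.3 separately excludes culture-negative randomised patients from the final analysis, and 6.2.2 lets cases be dropped when fewer than 5% are missing. Both also conflict with the no-subtraction rule. Correcting 4.4.6.1 does not resolve either, and they need their own decision.

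**What to change.** Make two changes before unblinding:

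1. In 4.4.6.1, replace the reference to participants who completed the trial. Say that after database lock the randomisation table is merged for every randomised participant, whether or not the trial was completed.
2. In 4.6, add that completion status is descriptive and does not decide membership of the ITT or safety set.

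The cost is one sentence in each of two sections. Nothing changes operationally, because the randomisation list already exists and data from withdrawn participants are already retained.

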4.4.6.2. Participant Randomization

This trial is a double-blind, placebo-controlled trial. IP and placebo randomization will be performed by the IP manufacturer using uneven-block randomization strategy with the following considerations:

- A computer-generated randomization list that provides an associated unique study identification number is produced by a researcher unrelated to the study/trial
- The randomization list is saved as a document in a format that assigns appropriate identifiers to the study subjects. This document is safely and securely kept by the Sponsor along with a log of the code used to generate the list.
- The randomization list is sent to the assigned person to preserve any and all blinding and concealment. The blinded investigators/research team should not see the randomization list during the running of the trial (see 6.6.3 for blinding).
- Randomization is double-blind, and the clinical trial site is not aware of the type of intervention (IP or placebo) that a particular patient will receive.

A procedure for emergency breaking the code is implemented by the sponsor and the icddr, Data Safety Monitoring Board (DSMB) in case there is a need for emergency access for the benefit of the participant.

4.4.6.3. Blinding and Unblinding

The blinding/randomization of the medication is determined when the individual patient study supplies are packaged by the IP manufacturer. Standard randomization methods are used, i.e. uneven block randomization. The study center is required to dispense the patient medication in chronological order to each of the patients entering the study. A sealed envelope containing the randomization code breaks will be given to the Investigator for safe keeping enabling easy access in the event of an emergency, requiring the code to be broken.

Management of Emergency Code Break:

The emergency code breaks will be placed by Hunazine Biotech in a sealed envelope and kept at the study center. The code must only be broken in the case of medical events which the investigator/physician in charge of the patient feels cannot be adequately treated without knowing the identity of the study medication.

Sponsor should be contacted before breaking the code. If it is not possible, and the situation is an emergency, the investigator may break the code and contact the Sponsor as soon as possible. The following information needs to be recorded in the event of an Emergency Code Break:

- Date of Code Break
- Identification of person(s) requesting the Code Break
- Reason for breaking the code
- Investigator Signature.

The person who broke the code must sign and date the envelope which, if opened at study site, will be returned to Safety Board (SB) by the SB site monitor. The patient will be withdrawn from the study.

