4.7.4. Recording AE, SAE and ADRs

All AEs, including local and systemic reactions not meeting the criteria for AE/SAEs/ADRs, will be captured on the appropriate Adverse Event Form. Information to be collected includes event description, time of onset, clinician's assessment of severity, relationship to study product (assessed only by those with the training and authority to make a diagnosis), and time of resolution/stabilization of the event.

All AEs occurring while on study must be documented appropriately regardless of relationship. All AEs will be followed to adequate resolution.

Any medical condition that is present at the time that the participant is screened will be considered as baseline and not reported as an AE. However, if the study participant's condition deteriorates at any time during the study, it will be recorded as an AE.

Changes in the severity of an AE will be documented to allow an assessment of the duration of the event at each level of severity to be performed. AEs characterized as intermittent require documentation of onset and duration of each episode.

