4.11. Discontinuation of Trial Intervention and Participant Withdrawal from Trial

Participants may withdraw from a research study for any reason, even without mentioning any reason. The participants will be able to receive standard treatment of the hospital without any penalty. For evaluation and reporting purposes, researchers may ask participants for their reasons for early withdrawal.

An investigator may discontinue trial intervention or withdraw a participant from the study for the following reasons:

- Significant study intervention non-compliance.
- If any adverse event (AE), Serious adverse events (SAE), laboratory abnormality, or other medical condition or situation occurs, continued participation in the study would not be in the best interest of the participant.
- Disease progression which requires discontinuation of the study intervention
- If the participant meets an exclusion criterion (either newly developed or not previously recognized) that precludes further study participation.
- Participant unable to receive study intervention for 3 days.
- Reporting over-dose
- protect a participant from excessive risk or risk with a demonstrated lack of benefits (e.g., a participant experiences serious side-effect without the anticipated therapeutic effects), or
- maintain the integrity of the data (e.g., a participant is not following study procedures or may be deliberately providing false information).

Whenever an investigator terminates a subject's participation in research, the investigator must explain to the participant the reasons for the termination and, as appropriate, other treatment options available to the participant.

The data to be collected at the time of study intervention discontinuation will include the following:

- Physical examination
- Vital signs
- Complete blood count (CBC)
- Blood Basic metabolic panel, including Serum electrolytes and creatinine
- Assessment of vomiting
- Assessment of stool output
- Assessment of dehydration
- Assessment of IV and oral ORS and oral water intake
- Assessment of urine output
- Administration of questionnaires or other instruments helping participants to register symptoms, such as stool charts.
- Assessment of adverse events.

Follow-up calls will be made with patients who completed the protocol with questionnaires focusing on the side effects. Calls will be made once a week during the 28-day follow-up period.

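### An emergency code break automatically ends study observation, so later outcomes go missing because of a medical event that may depend on arm

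*Combined protocol and SAP*

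**What the plan says.** Section 4.4.6.3 restricts emergency unblinding to events whose treatment depends on the allocation being known: "The code must only be broken in the case of medical events which the investigator/physician in charge of the patient feels cannot be adequately treated". After listing what must be recorded, it adds, without exception: "The patient will be withdrawn from the study". The rule refers to the study, not to study drug.

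Other sections bear on what happens next:

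- **4.11** treats stopping the intervention and withdrawing a participant as two separate actions, and makes both discretionary. One listed reason is an adverse event, serious adverse event or other medical condition. It sets one assessment: "The data to be collected at the time of study intervention discontinuation will include the following", and the list includes stool output, fluids and adverse events. On later contact it says: "Follow-up calls will be made with patients who completed the protocol with questionnaires focusing on the side effects", weekly over 28 days.
- **4.4.6.1**: "data from all participants who have completed the trials will be assigned to the Group A (VR-AD-1005 intervention) or Group B (placebo) for analysis".
- **4.7.4**: "All AEs occurring while on study must be documented appropriately regardless of relationship", and also "All AEs will be followed to adequate resolution".
- **6.2.1**, repeated in 6.3: "No subtractions will be made from the ITT group after randomization assignment".
- **6.2.2** classifies missing data as MCAR or MAR. It lets the researcher drop cases when they are under 5% of the sample, and otherwise uses multiple imputation in the ITT population.
- **6.4** uses all participants per arm as the denominator for the proportions with an AE or SAE.

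**The concern.** Stopping a drug and stopping observation are different decisions, and 4.4.6.3 makes the second one automatic. The trigger is a medical event after randomisation, and its frequency may differ between VR-AD-1005 and placebo. If observation stops there, the stool, rehydration and recovery outcomes after the code break are missing for a reason that may be related both to arm and to outcome. That is hard to defend as MCAR or MAR.

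On the safety side, a new event after withdrawal could go unrecorded while the patient still counts in the denominator, which would understate the AE proportion in that arm.

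There is also a practical problem. After a code break, site staff cannot tell from the text whether to go on weighing stool and charting fluids, or whether to make the follow-up calls.

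**Working it through.** **1. Following a code-broken patient through the text**

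- *Stool and rehydration.* Section 4.5.2 ties stool collection and fluid recording to the duration of treatment. Section 4.11 adds one assessment at discontinuation. No section continues the 12-hourly collection for a patient who has been withdrawn. Data up to the code break, and that one assessment, do exist.
- *The triggering event.* Section 4.7.4 requires it to be followed to resolution, and 4.7.5 and 6.4 require reporting of serious events. This follow-up survives withdrawal.
- *New adverse events.* Section 4.7.4 sets the recording window as time on study. A withdrawn patient is outside it.
- *Calls to day 28.* Section 4.11 describes them for protocol completers. Section 4.6 defines completion as all phases through the last scheduled procedure, which a withdrawn patient does not reach. Section 4.12 mentions an in-person visit for withdrawals, but no section schedules one.
- *Analysis.* Section 6.2.1 keeps the patient in the ITT set, whereas 4.4.6.1, as worded, attaches arm labels to the data of completers. Section 6.2.2 either drops or imputes the missing values. Section 4.11 bars replacement once the patient has been dosed.
- *Withdrawal rule.* It is automatic in 4.4.6.3 and discretionary in 4.11.

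**2. The plan's own figure**

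Inputs from section 5.0: mean 280 g/kg, SD 156 g/kg, 33% reduction, two-tailed t-test, alpha 5%.

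- Difference: 0.33 × 280 = 92.4 g/kg.
- Noncentrality: 92.4 / (156 × √(2/n)), which is 2.96 at n = 50 and 3.63 at n = 75 per arm.
- Exact noncentral-t power: 0.835 at 50 per arm (stated 0.82) and 0.950 at 75 per arm (stated 0.94). Both are reproduced to within 2 points.

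**3. Effect on power (numbers lost are assumed)**

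- The 5% limit is 0.05 × 150 = 7.5, so at most 7 cases (4.7%) may be dropped.
- Losing 1, 3 or 7 of 150, split as evenly as possible, gives power 0.949, 0.946 or 0.940, against 0.950 with none lost.

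**4. Effect on the arm mean (assumed illustration)**

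If k of 75 patients in one arm are dropped and their output lies x SD above that of the remaining patients, the arm mean is understated by k × x × 156 / 75 g/kg.

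| k | x = 1 | x = 2 | share of 92.4 g/kg |
|---|---|---|---|
| 1 | 2.08 | 4.16 | 2.3% to 4.5% |
| 3 | 6.24 | 12.48 | 6.8% to 13.5% |

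If their output were lower, the shift would reverse. Similar losses in both arms would largely cancel in the difference.

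**The case against.** The best case for the plan is that its other sections already protect these patients, and that the event is rare. Much of this stands, and it rules out several stronger readings.

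- **Removal from ITT.** A reader might infer that the rule removes the patient from the ITT set. It does not. Sections 6.2.1 and 6.3 protect membership; withdrawal only leaves later values missing, and 6.2.2 has a route for imputing them.
- **Loss of the triggering SAE.** A reader might infer that the event behind the code break loses its follow-up. Section 4.7.4 requires follow-up to resolution with no exception for withdrawn patients, 4.7.5 requires SAEs to reach the DSMB within 24 hours, and 6.4 reports outcome and duration for each SAE. The gap concerns new events.
- **No further contact at all.** Sections 4.3 and 4.9 describe the weekly calls for discharged participants generally; only 4.11 words them for completers. Whether a withdrawn patient is called is therefore unresolved, not excluded.
- **Absence from 4.11.** A code break is not listed there by name, but its trigger overlaps the listed AE, SAE or medical-condition reason. The real difference is automatic against discretionary.
- **Worst purgers, or most of the safety data.** Nothing in the documents says that code-broken patients would have the highest output: 4.9 manages purging in every patient without reference to arm. No code-break or SAE rate is given, and there may be no code breaks at all.
- **The 5% rule.** It counts all missing cases, not code breaks alone. If total missingness reaches 5%, imputation applies instead of dropping.

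What the objection does not answer is that no section continues stool and rehydration measurement after the withdrawal that 4.4.6.3 orders, and that 4.4.6.1 and 4.11 are worded for completers. Imputation under MAR is also a weak remedy for data that need not be missing.

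**Conclusion.** The point holds as a defect in the observation rule. An automatic withdrawal from the study, triggered by a post-randomisation medical event, creates avoidable missing outcomes that may depend on arm, and the sections governing withdrawal, follow-up and group assignment do not agree.

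The numerical effect is probably small. Power barely changes. The shift of about 2 to 12 g/kg rests on three assumptions that the documents do not supply: 1 to 3 code breaks, all in one arm; outputs 1 to 2 SD above the rest; and the cases being dropped, not imputed. The stronger case for a change is that even a single code-broken patient leaves staff and analysts without a consistent instruction, and may have later adverse events that go unrecorded while counting in the denominator. This conclusion takes no view on how study drug should be handled after a code break.

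**What to change.** Replace the withdrawal sentence in 4.4.6.3 with a statement that:

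- a code break is not by itself a reason for withdrawal from the study;
- whatever is decided about study drug, and unless the patient withdraws consent, stool, rehydration and adverse-event data are collected as far as feasible to 72 hours, and adverse-event follow-up continues to day 28;
- the patient is analysed as randomised in the ITT and safety analyses, with the code break flagged for a sensitivity analysis.

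Then bring the related text into line: the withdrawal reasons and the follow-up calls in 4.11, and the completer wording in 4.4.6.1, so that every randomised participant's data are assigned to an arm.

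The cost is a short amendment to three sections, with no change to sample size. Two downsides should be acknowledged. Later assessments in these few patients would be unblinded, although stool weight is an objective measure and the flag allows a sensitivity analysis. Weighed stool may also be unobtainable if the patient is referred elsewhere, which is why the wording says as far as feasible.
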